During the study period (12-weeks), all participants will complete a weekly diary and the Self-Harm Incidents' Log (Participants), alone, with a trusted peer, or with the research assistant. They will also complete the Concomitant Therapies Form with a research assistant. The diary will include any thoughts of self-harm that have occurred since the last diary date, and any life events which have influenced their self-harm (including the time spent outside their cell). The Self-Harm Incidents' Log (Participants) will include incidents of self-harm in the last week and the severity of the incidents of self-harm. The Concomitant Therapies Form will contain information on any new therapy that has been started during the study period. Information in the Self-Harm Incidents' Log (Participants), will be cross checked with information from prison records (e.g. self-harm incidents databases) and SystmOne using the relevant Self-Harm Incidents' Logs. Concomitant Medications will be recorded from SystmOne on the concomitant therapies this information will be checked using the relevant details for the concomitant therapies this information will be checked using the relevant prison or healthcare databases. We shall also collect the dates and duration of time that women spent on a basic regime during the intervention period from NOMIS on the Basic Regime Data Collection Form.

At 8-weeks and 12-weeks, all participants will complete the secondary outcome measures (BSS; BDI-II; BHS; RSE; WEMWBS) and the health related quality of life scales (EQ-5D-5L; SF-12) and we shall record on the ACCT Status Form whether or not they are participating in the ACCT process.

If a participant is transferred part way through the research, we will seek permission from the receiving prison to complete the ongoing measures (e.g. concomitant medication) and the follow up measures. This will require local access to prison and healthcare databases. We will seek permission from the

WORSHIP III	IRAS No: 241606

participant in the consent process to contact their probation office / CRC for help to locate the women to try to complete ongoing and follow up measures.

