- Long-term follow up assessments at 12-weeks will be collected during a 1-hour interview with a blind outcome assessor and will include all secondary outcome measures (BSS; BDI-II; BHS; RSE; WEMWBS) and the health related quality of life measures (EQ-5D-5L; SF-12).
- The participant's ACCT status will be recorded by the research assistant.
- We shall also collect from NOMIS the amount of time that each participant spent on a basic regime from 8 weeks to 12 weeks.

Prison-level data collection

We shall collect the following information on the Prison-Level data collection form:

- The average amount of time that women spend outside their cells for each of the study prisons in one week
- Whether the prison provides an in-cell telephone service.

Qualitative assessments

12-20 individual interviews (6-10 from the control group and 6-10 from the intervention group) will be completed with pilot women at 10-12-weeks to determine if there are any issues or problems with participation which need to be addressed before the full-scale trial. These interviews are designed to help to inform the decision regarding progression, for example, if a rescue plan is necessary.

During the full-scale trial, process evaluation interviews will be completed with 40 women prisoners (20 from the intervention group and 20 from the control group) at 10-12-weeks. These interviews will be designed to explore the opinions of the participants on PIT or TAU and any problems they encountered in relation to the implementation of the intervention in the prison. Staff process evaluation focus groups will be undertaken in all prisons (N=7; 8-12 per group) to explore their perceptions of TAU or PIT, for example, how they believe it affects the wellbeing of women in their care and any problems they encountered in relation to implementation of the treatment in their prison.

We will invite the therapists, research assistants and the outcome assessors to take part in individual qualitative process evaluation interviews.

Withdrawal and termination criteria

Women will be removed from the research if they wish to withdraw e.g. if they are finding participation too distressing. All women who withdraw will be asked to provide a reason. In WORSHIP II we found that approximately 65% of the women were happy to disclose why they no longer wished to participate

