The therapists in the research will be using an adapted version of PIT. The adaptation of the intervention, and its delivery, took place during WORSHIP I and II. Originally, PIT was a 4-session intervention which had been delivered to people in the community who repeatedly self-harm and attend A&E. In its original form, PIT is not designed to be either specific to women, or gender sensitive. Neither is it designed to
be used with prisoners who have complex histories including domestic abuse, sexual assault and childhood neglect. Any version of PIT delivered in prison needs to be mindful of the women's difficult histories and address problems specific to being incarcerated, such as loss of contact with their family or prison-based conflict.

Following consultation with women in prison and staff in WORSHIP I, the intervention training and supervision were adapted so they had more emphasis on our target group e.g. prison-specific case studies were used during the training, and supervision emphasised women's experiences of incarceration. During the PIT sessions with women prisoners, the therapists were encouraged to acknowledge the likely sources of trauma in women's lives both as precipitants, as well as maintaining factors in their self-harm. At the beginning of sessions, therapists specifically identified with clients such possible traumatic and triggering events; events which were considered particularly difficult for some of the prisoners to manage. For example, they discussed the links between being separated from children, being abused or perceived as abused by other prisoners, being frightened in the first night or first weeks of imprisonment and being isolated for long periods in cells alone as powerful potential triggers for self-harm.

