In terms of healthcare interventions, provision ranges from low-intensity talking therapy to complex psychiatric interventions. Most of the prisons offer Cognitive Behavioural Therapy (CBT), traumafocused approaches and group-based therapies although they are unlikely to be specifically targeted for self-harm. Dialectical Behavioural Therapy or DBT informed-therapy is offered in at least seven prisons. DBT is designed for treatment of borderline personality disorder but contains elements which are specifically targeted at self-harm. Two prisons provide specialised services for women with personality disorders, e.g. the 'Options' service at HMP Downview, which delivers DBT, and the 'ADAPT' team at HMP Styal. ADAPT is part of the Offender Personality Disorder (OPD) pathway which is aimed at offenders with severe personality disorder who pose a high risk of harm to others or of reoffending in a harmful way [42]. One of the main aims of the ADAPT team is to increase the confidence and competency of a wide range of prison and partner agency staff to support women who have personality difficulties to improve their psychological health and wellbeing and reduce reoffending. The ADAPT team, therefore, works closely with staff (rather than providing individual or group therapy for women) and provides training, supervision and reflective practice for prison staff, as well as joint development of formulations involving prisoners and staff. The model of the ADAPT service is that of mainly psychologically-informed consultation, support and liaison with prison staff of all grades and disciplines. Various other initiatives are offered in individual prisons e.g. the 'Reader Project' in HMP New Hall which uses approved texts to open discussion about emotion, self-esteem, talk about death and grief, whilst building women's confidence and literacy skills. None of the treatments that are currently run in prison has been modified to be targeted at self-harm and its underlying problems specifically; and none has been formally evaluated; let alone using an RCT design. All prison-based initiatives depend on availability of trained staff and are currently under-resourced [7].

Term	Definition	
Adverse Event (AE)	Any untoward medical occurrence in a participant including occurrences which are not necessarily caused by or related to the intervention or research.	

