The WORSHIP III study investigates the use of PIT with vulnerable high-risk women in prison who selfharm. WORSHIP III not only undertakes research in a high-risk environment, but also may recruit women in prison very early into their admission to a prison. Both these factors mean our participants are likely to self-harm in the context of the study period and self-harm is our primary outcome. In the context of this study, therefore, self-harm is an expected event. As such, we do not necessarily consider that self-harming behaviour represents an adverse event. A number of complex intersecting variables are associated with risk of an individual undertaking self-harming behaviour. All of our participants are women who have very recent histories of self-harming behaviour in response to life circumstances. Therefore, to determine whether an incident of self-harm needs to be investigated and reported during the study we follow the procedure outlined below.

Adverse Events Process

Each participant's personal officer, Safer Custody, healthcare and the OMU will be informed that the participant is taking place in the study. They will be asked to report any changes to a participant's self-harm behaviour to the research team. Changes may include increased frequency of self-harm, a change in the method of self-harm (e.g. to a more risky type) and undertaking self-harm that: results in death; is life threatening; requires an admission to hospital or prolongation of existing hospitalisation; results in persistent or significant disability or incapacity; or is medically significant, i.e. requires intervention to prevent any one of the above outcomes. The research assistant will also be monitoring the participant's self-harm on a weekly basis and can alert the trial manager if they notice any changes in the self-harm behaviour.

Prison and healthcare staff will also be asked to report to the team any non-self-harm adverse events. The research assistant will also ask the participants each week if they have experienced any new health problems, aside from self-harm incidents, so they can be investigated to see if they are adverse events. These adverse events will be recorded on the paper Adverse Events Form Not Self-Harm and entered into the CTU database Adverse Events Log.

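### The weekly adverse-event question asks women only about new health problems, which is narrower than the protocol's own adverse-event definition and does not prompt for worsening of existing conditions

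*Protocol*

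**What the plan says.** The table at the start of the Adverse Events section defines an adverse event as "Any untoward medical occurrence in a participant including occurrences which are not necessarily caused by or related to the intervention or research". Worsening is not named, but the wording is broad enough to include it.

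Adverse Events Process then sets out how events come to light:

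- **Women in the trial, weekly:** "The research assistant will also ask the participants each week if they have experienced any new health problems, aside from self-harm incidents", and the answers are looked into as possible adverse events.
- **Staff:** "Prison and healthcare staff will also be asked to report to the team any non-self-harm adverse events".
- **Self-harm:** this has its own route. Staff report changes, including higher frequency or a riskier method, and "The research assistant will also be monitoring the participant's self-harm on a weekly basis and can alert the trial manager".
- **Women who are released:** they receive a letter asking them to make contact about any adverse event.

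Under Responsibilities, adverse events feed a quarterly review for trends and reports to the sponsor and oversight committees.

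**The concern.** The weekly question is the one regular occasion on which a woman is asked directly about harm other than self-harm, and it is limited to problems that are new. The population makes that limit matter. Eligibility requires a current or recent ACCT and self-harm within the last month. The planned baseline table records past depression, anxiety, post-traumatic stress disorder and personality disorder. The Rationale describes extensive histories of victimisation and multiple trauma.

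Trial Treatments says that in the adapted therapy "therapists specifically identified with clients such possible traumatic and triggering events", and the section on assessment and management of risk accepts that women may become distressed in sessions. If taking part made someone worse, an existing problem becoming more severe is a plausible form for it. A woman whose known depression or trauma symptoms have deteriorated could answer honestly that she has no new problem. The quarterly trend review and the final account of harms would then rest on an incomplete count.

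**Working it through.** The protocol states no adverse-event rate, so there is no figure to reproduce. The check is a comparison of texts.

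**1. Is the prompt narrower than the definition and the other prompts?**

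| Source | Scope | Limited to new? |
|---|---|---|
| Adverse-event definition | any untoward occurrence, related or not | No |
| Staff reports | any adverse event other than self-harm | No |
| Letter to released women | any adverse event | No |
| Self-harm monitoring | changes, including worsening | No |
| Weekly question to women | new health problems other than self-harm | Yes |

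The weekly question is the only one of the five with this limit.

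**2. What else would pick up worsening?**

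| Route | Covers | Stated link to the adverse-event log |
|---|---|---|
| BSS, BDI-II, BHS at baseline, 8 and 12 weeks, both arms | suicidal ideation, depression, hopelessness | None |
| Weekly diary item, both arms | frequency of self-harm thoughts | None |
| Mandatory disclosure of risk to the prison | intention to self-harm or die by suicide | None |
| Staff reports | whatever reaches staff | Yes |
| Repeated trauma-symptom scale | not listed | Not applicable |

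So depression and suicidality are measured by self-report, but a deterioration on those measures is not said to enter the adverse-event process. Trauma symptoms have no repeated measure.

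**3. Do the scales substitute for the question?** Only in part. They are taken twice after baseline, and the protocol's analysis section reports them as adjusted mean differences, which do not count women who deteriorated. The sample-size section allows 20% attrition on secondary outcomes, and the Consent section stops all data collection after formal withdrawal. A woman who leaves before week 8 may have no follow-up score, whereas a weekly question could have recorded her worsening before she left.

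**4. Illustration only.** Every rate here is an assumption; only n = 132 per arm is the protocol's. Suppose worsening occurs in 10% of usual-treatment women and 20% of PIT women, no other route records it, and the weekly question captures all, half or one fifth. With p̄ the mean of p1 and p2, two-sided 5% power is

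Φ{ [ |p2 − p1| − 1.96·√(2p̄(1−p̄)/n) ] / √([p1(1−p1) + p2(1−p2)]/n) }.

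- All (10% v 20%, 13.2 v 26.4 expected): (0.10 − 1.96 × 0.0440)/0.0435 = 0.32, power about 63%.
- Half (5% v 10%, 6.6 v 13.2): (0.05 − 1.96 × 0.0324)/0.0323 = −0.42, about 34%.
- One fifth (2% v 4%, 2.6 v 5.3): (0.02 − 1.96 × 0.0210)/0.0210 = −1.01, about 16%.

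Loss of capture makes a difference harder to see. With equal capture in both arms, the expected ratio stays at two to one.

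**The case against.** The strongest reply is that deterioration is well observed in this trial. Depression, suicidal ideation and hopelessness are self-reported in both arms, with assessors blind to allocation at follow-up. Staff may report any adverse event other than self-harm, and research assistants must pass on any event they are told of or identify. Asked every week, *new* can mean new since last week, and the protocol describes the question rather than reproducing the form. Much of this stands, and it rules out several stronger readings that a reader might infer:

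- **That worsening depression and suicidality go unmeasured.** They do not; what is missing is a stated link from those measures to the adverse-event log.
- **That leaving self-harm out of the question is a gap.** It is not, because self-harm has its own weekly log and monitoring.
- **That staff reports are undermined because some women hide self-harm from staff.** The protocol says this to justify advertising for recruitment; it does not concern other kinds of deterioration.
- **That the protocol expects PIT to cause psychological harm.** It names only upset or distress. "Women will be removed from the research if they wish to withdraw e.g. if they are finding participation too distressing" gives one example of a reason to withdraw and refers to participation as a whole. The passage on triggering events describes how the therapy was adapted in the earlier pilots.
- **That harms are under-counted, or would look alike in the two arms.** No document figure shows an under-count, and the illustration keeps the ratio between arms.

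The mismatch between the weekly question and the definition survives. The ambiguity of *new* is itself a reason to settle the wording.

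**Conclusion.** The point holds as a mismatch in adverse-event ascertainment: the women's own weekly prompt is narrower than the definition it serves and than every parallel prompt. Taken at its word, it does not ask about worsening of existing conditions. Other routes cover part of this for depression and suicidality, and less for trauma symptoms. Under-ascertainment is a plausible risk of unknown size. The conclusion assumes that the form follows the protocol's description and that *new* is read in its ordinary sense. This is a low-cost improvement to safety reporting and has no bearing on the primary analysis.

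**What to change.** In Adverse Events Process, and on the form used each week, ask about *any new or worsened physical or mental health problem, aside from self-harm incidents*. Keep the separate self-harm log unchanged.

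It would also help to state whether a worse BSS, BDI-II or BHS score, a diary answer or a risk disclosure is to be assessed as a possible adverse event.

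Optionally, tabulate by arm the number of women whose BSS or BDI-II score at 8 or 12 weeks is worse than baseline by a pre-set amount. These data are already collected, and the table may properly belong in the statistical analysis plan, which was not available here, so its absence from the protocol is not a fault.

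The cost is one wording change, with somewhat more adverse-event reports to log and assess.

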[name] will help coordinate therapist recruitment and retention. She is a Consultant Clinical Psychologist and Lead Psychologist for Offender Care in Central and North West London NHS Foundation Trust.

Patient and Public Involvement:

[name] and [name] are experts-by experience. Our experts by experience have shaped study design and edited the grant application and plain English summary. They have also suggested ways in which prisoners and staff might be involved in the research, emphasising the role of prisoners in understanding the prison system.

KEY WORDS:

Prison; self-harm; women; psychodynamic interpersonal therapy; pragmatic trial

	IRAS No: 241606
WORSHIP III	

TRIAL FLOW CHART

	IRAS No: 241606	
WORSHIP III		

BACKGROUND

WORSHIP III is a full-scale, randomised controlled trial to examine the clinical and cost-effectiveness of modified Psychodynamic Interpersonal Therapy (PIT) for women who self-harm in prison. Self-harm is a complex behaviour associated with acute psychological distress and increased suicide risk [1;2]. The most common self-harm methods in women's prisons are cutting or scratching, followed by strangulation [1]. Self-harm is more prevalent in women's prisons with 1987 incidents per 1000 women, compared to 399 per 1000 men, over 12 months [3].

NICE recently examined which interventions were effective for adults in the criminal justice system who self-harm. The review, limited to systematic reviews and RCTs, found no prison-based RCTs which specifically evaluated self-harm interventions with self-harm rates as the primary outcome (NICE's recommended measure [4]).

In preparation for this grant, we conducted our own systematic review of current self-harm interventions in forensic settings (women's prisons and secure hospitals) including all experimental designs. The inclusion and exclusion criteria for the review were:

Inclusion criteria:

- Include participants who were women, over the age of 18, and residing in a secure forensic mental health service or a prison.
- Examine the outcome of an intervention.
- If participants in the study included men and women, women were analysed separately.
- Measures the number of self-harm incidents as an outcome
- Report on original data.
- The paper must be written in English.
- The paper must be published.

Exclusion criteria:

- They did not include women.

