Of 3968 women in prison in England/Wales [16] at any one time, approximately one third self-harm. Nearly 9000 women pass through prison every year; [17] this means that evidence-based interventions have the potential to benefit several thousand women annually. Furthermore, if benefits are sustained, this is likely to have positive effects on their families in the community. In addition, fellow prisoners who do not self-harm may be adversely affected [18] as well as staff who witness a high level of self-harm [19; 20]. Therefore, effective treatment is likely to have a positive effect on wellbeing of the wider prison community. An intervention which lessens the burden on staff, as well as women in prison, is particularly important given the current discontent of prison officers with conditions in UK prisons [21].

Assessment and management of risk

Women prisoners in the trial

All research in the Women's Estate needs approval from Her Majesty's Prison and Probation Service (HMPPS) who state that researchers must disclose the following things:

- Behaviour that is against prison rules
- Information that either indicates a risk or harm to yourself or others
- Information on previously undisclosed illegal acts or plans to commit a new
- crime
- Information that raises concerns about terrorist, radicalisations, or security issues.
- information about poor or unacceptable practices by the prison staff or by an outside organisation

As such, we are required to disclose information on issues such as ongoing abuse of a child or adult, and information on intention to self-harm or commit suicide. This requirement will be made explicit to participants during consent. If participants do not agree to these disclosures they will not be able to take part in the research. We have followed this guidance in all previous research in prisons over the last 20+ years and, as far as we are aware, the potential for disclosure rarely prevents women from participating. It is our understanding from WORSHIP II that the women find disclosure of risk a containing element of their relationship with the therapist/researcher which indicates that they are taking the woman's complex needs seriously and are committed to protecting them and other people from harm. Disclosures are made to all relevant departments in the prison including Safer Custody staff, healthcare staff, personal officers and the Offender Management Unit (OMU). All these personnel have

	IRAS No: 241606	
WORSHIP III		

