An opportunity sample of 264 women will be recruited to the research. The sample size is powered to detect a minimal important clinical difference of 33% reduction in self-harm incidents over 8 weeks. This clinically significant difference is based on Hawton et al's systematic review of the efficacy of psychological and pharmacological interventions designed to reduce self-harm repetition [43]. From MOJ prison data, the average number of self-harm episodes over 8 weeks in the control group was 6.65 [3]. We modelled this with a Poisson distribution (mean and variance=6.65) and used Monte Carlo simulations with 1000 simulations to estimate the power for a range of sample sizes, with power defined as the proportion of estimated p-values less than 0.05 for null hypothesis testing (treatment effect is 0), against an alternative hypothesis (33% reduction in the log of the outcome). With 5% significance, to obtain 90% power, we will require 105 per group for the primary analyses. Based on WORSHIP II [6] we estimate 20% attrition so will recruit 132 per group at baseline. This level of attrition is not expected in the primary outcome, due to availability of prison data and the fact that self-reported incidents will be measured on a weekly basis, but allows for attrition in the secondary outcomes.

We expect that there will be several potential therapists because we are using trainees as well as qualified professionals. This means that each therapist will see a small number of participants each (mean≈6.6). In turn, we expect that the ICC will be small (though no estimates are available to inform our calculations), and since the number of participants per cluster is also small, the corresponding design effect indicates a small increase to the sample size would be required to take into account this clustering. We anticipate that this will be balanced by accounting for baseline prognostic factors in our statistical models, and that 90% power will be maintained with lower than 20% attrition rate for the primary outcome. We shall include a random effect for each therapist within the statistical analysis models.

Planned recruitment rate

The predicted figures have been calculated based on the number of women who will pass through each of the prisons, depending on their size and the recruitment rate achieved in WORSHIP II. The predicted figures (confirmed by HMPPS) are calculated as follows:

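### The control mean of 6.65 self-harm episodes in 8 weeks cannot be reconciled with the protocol's own rates under the stated Poisson model, and 105 per group does not follow from it, so the 90% power is unsupported.

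*Protocol*

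**What the plan says.** The section on sample size calculation in the protocol takes its base rate from Ministry of Justice prison data: "the average number of self-harm episodes over 8 weeks in the control group was 6.65 [3". It continues: "We modelled this with a Poisson distribution (mean and variance=6.65". The target is a "minimal important clinical difference of 33% reduction in self-harm incidents over 8 weeks", but the simulation is described as testing "against an alternative hypothesis (33% reduction in the log of the outcome". The result is "With 5% significance, to obtain 90% power, we will require 105 per group for the primary analyses", and then "we estimate 20% attrition so will recruit 132 per group at baseline".

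Two other places bear on the base rate. The Background reports "1987 incidents per 1000 women, compared to 399 per 1000 men, over 12 months [3", citing the same source as the 6.65. The Rationale says: "Of 3968 women in prison in England/Wales [16] at any one time, approximately one third self-harm".

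The protocol does not show how 6.65 was obtained or which women it covers. It also does not explain how routine prison statistics come to contain a control group.

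**The concern.** The base rate and the annual rate carry the same citation but sit far apart. The section on sample size calculation assumes that the variance equals the mean. Power for a rate ratio depends on the expected number of events and on the spread between women, so both assumptions drive the claim of 90%.

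If the true 8-week mean is near 1, or if it is high only because a few women contribute most incidents, 105 per group does not give 90% power for a 33% reduction. At a mean of 0.92 and 105 per group, the reduction detectable with 90% power would be about 42% under Poisson and about 52% with a negative binomial dispersion of 1. A null result could then be read as evidence against the therapy when the trial could not have seen the effect it was designed for.

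**Working it through.** **Inputs from the protocol.** Control mean 6.65 per 8 weeks, variance 6.65, 33% reduction (rate ratio RR = 0.67), 5% significance, 90% power, 105 per group and 132 recruited (sample size calculation); 1.987 incidents per woman per 12 months (Background); about one third of women self-harm (Rationale); self-harm in the last month required (eligibility criteria). Two-sided testing is assumed because sidedness is not stated.

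**1. The plan's own figure.** For a Wald test on the log rate ratio with control mean m and dispersion k (k = 0 is Poisson),

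n per group = (1.96 + 1.2816)² × [1/m + 1/(0.67m) + 2k] / (ln 0.67)².

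With m = 6.65 and k = 0: 10.51 × (0.1504 + 0.2244) / 0.1604 = 24.6, so about 25 per group. A simulation of 20,000 trials gave 92% power at 25 per group. At 105 the power exceeds 99.9%.

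The description of the effect as a reduction in the log does not rescue 105:
- RR = exp(−0.33) = 0.72 gives 35 per group.
- A 33% cut in the log mean (6.65 falling to 3.56) gives 12 per group.

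Solving the formula for n = 105 requires m of about 1.56 under Poisson, or k of about 0.61 at m = 6.65. Neither is stated. Only the attrition step reproduces: 105 / 0.8 = 131.25, rounded up to 132.

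**2. The base rate against the protocol's other rates.**
- Per self-harming woman: 1.987 × 3 = 5.96 per year; × 8/52 = 0.92 per 8 weeks.
- Ratio: 6.65 / 0.917 = 7.25.
- 6.65 per 8 weeks is 6.65 × 52/8 = 43.2 per woman-year. At that rate, 1.987 / 43.2 = 4.6% of women would account for every recorded incident.
- If 6.65 were annual, the implied share of women self-harming would be 1.987 / 6.65 = 30%, and the 8-week mean 6.65 × 8/52 = 1.02.

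**3. Can eligibility close the gap?** Illustrative assumption: annual rates among self-harming women are gamma with mean 5.96 and shape s (scale θ = 5.96/s), and women enter only with at least one incident in the last month (t = 1/12). With P0 = (1 + θt)^(−s), the mean annual rate after selection is

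5.96 × [1 − (1 + θt)^(−s−1)] / (1 − P0).

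For s = 1, θt = 0.497 and P0 = 0.668, which gives 5.96 × (1 − 0.446) / 0.332 = 9.94 per year, or 1.53 per 8 weeks. The variance follows in the same way from the second moment.

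| Shape s | 8-week mean | Variance / mean | k | Power at 105 / 132 |
|---|---|---|---|---|
| 1 | 1.53 | 1.8 | 0.52 | 71% / 80% |
| 0.5 | 2.03 | 2.5 | 0.73 | 71% / 80% |
| 0.1 | 4.82 | 7.6 | 1.38 | 62% / 72% |
| 0.06 | 6.65 | 12 | 1.67 | 57% / 67% |
| 0.05 | 7.48 | 14 | 1.78 | 55% / 64% |

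A variant that fits all women (mean 1.987 per year, 25% to 33% self-harming in a year) gives means of 1.6 to 2.3, k of about 0.95 to 1.1, and power of 60% to 62% at 105 and 70% to 72% at 132. So moderate spread gives about 1.5 to 2. Means in the region of 6.65 (4.8 to 7.5 in the table) need a variance of roughly 8 to 14 times the mean.

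**4. Power without enrichment.** Power = Φ(|ln 0.67| / √{[1/m + 1/(0.67m) + 2k]/n} − 1.96).

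| Scenario | 105 per group | 132 per group |
|---|---|---|
| m = 0.92, Poisson | 70% | 80% |
| m = 1.02, Poisson | 75% | 84% |
| m = 1.56, Poisson | 90% | 95% |
| m = 6.65, k = 1 | 76% | 85% |

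**The case against.** The strongest reply is that the rates describe different women. The annual figure covers all women in prison and recorded incidents. The trial enrols women who self-harmed in the last month and are or recently were under ACCT monitoring, and its outcome adds self-report to several record systems because a single source may undercount. Both push the mean up, the second by an amount the documents do not give. This stands: the seven-fold gap is not a strict contradiction. It does not rescue the paragraph, because selection strong enough to reach 6.65 brings a spread between women that the stated variance rules out.

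A reader might also infer that 6.65 is an annual figure entered as an 8-week one. The 30% match makes that plausible, but the protocol says 8 weeks and the source is not at hand. The conversion to 1.02 also assumes a full year in custody. With 3968 women at any one time and about 9000 passing through each year, average time served is about 0.44 year, and 6.65 over that time would be about 6.65 × 8 / (0.44 × 52) = 2.3 per 8 weeks. Under Poisson, 2.3 would give about 98% power at 105 per group.

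Finally, much of the loss in the enriched scenarios comes from overdispersion rather than from a low mean, and the protocol does not expect 20% attrition for the primary outcome. Analysed numbers should therefore lie nearer 132 than 105. Both points are fair, and power is shown at both sizes for that reason.

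**Conclusion.** The point holds as a failure of internal consistency. A mean of 6.65, a variance equal to it, 105 per group and 90% power do not fit together, and the mean and variance do not sit with the protocol's own annual rate unless an unstated derivation is supplied. The stated 90% is therefore unsupported.

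It is not shown that the trial is underpowered, nor that 105 rests on a wrong base rate, since 105 cannot be traced to 6.65 at all. The size of any loss is conditional. Power at 105 / 132 per group is 70% / 80% at a Poisson mean of 0.92, 75% / 84% at 1.02, and about 55% to 76% / 64% to 85% across the enriched or overdispersed scenarios. A Poisson mean of 1.56 or more would keep at least 90%.

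These figures assume a two-sided 5% test, a rate ratio of 0.67, equal dispersion in both arms, no therapist clustering and no covariate adjustment. The enriched scenarios also assume gamma-distributed rates and make no allowance for added self-report.

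**What to change.** 1. Check 6.65 against the source table, and state its period, its population and how it was derived.
2. Re-run the simulation with a justified 8-week mean and dispersion for women who meet the eligibility criteria. State the effect once, as a rate ratio.
3. Check both inputs against the pooled, arm-blind 8-week counts from the internal pilot (43 women planned). With equal allocation and a rate ratio of 0.67 the pooled mean is 0.835 times the control mean: about 5.6 if 6.65 is right and about 0.8 if 0.92 is right. Even 43 women should separate these.
4. Restate the power, or the reduction detectable with 90% power, for the fixed 264 women.

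The cost is one source check, one re-run and a rewritten paragraph, with no extra enrolment. The downside is that the stated power may become less favourable.
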